Finally, the systematic review of the literature performed for the development of the national guidelines reveals a lack of evidence for chronic disease models of obesity care rather than models of care that focus on weight loss as the main goal of care (NHMRC, 2013). Chronic disease models of care are of particular relevance to patients with obesity and type 2 diabetes as the likelihood of sustained weight loss in this patient group, even with surgical intervention, has been shown to be low (NHMRC 2013; National Institute for Health and Care Excellence, 2013). It is therefore essential that the secondary complications of obesity (sleep apnoea, hypercholesterolaemia, hypertension, malignancy, infertility, non-alcoholic steatohepatitis, osteoarthritis) (ADIPS 2013; National Cancer Institute 2013; NHMRC, 2013) are identified early and managed effectively in these patients as sustained weight loss is unlikely in spite of weight reduction therapies (NHMRC 2013; National Institute for Health and Care Excellence, 2013).

Study Goals and Objectives

AIM

The aim of this study is to assess the feasibility, acceptability and effectiveness of a rural, multidisciplinary team-based approach to care for adult patients with diabetes mellitus and obesity.

OBJECTIVES OF THIS PROJECT

- To determine if a multidisciplinary multi-intervention clinic for obesity tailored to the individual can reduce absolute cardiovascular and morbidity risk
- To evaluate management and treatment factors as potential predictors of outcome
- To determine whether an interdisciplinary multi-intervention obesity clinic for people with diabetes improves metabolic profile
- To provide process and impact outcomes to substantiate and drive clinical and policy change supportive of a multidisciplinary systematic approach for patients living with obesity

OUTCOMES

Primary Outcome:	change in HbA1c (measured as a continuous variable) in the intervention group compared with the control group
Timepoint:	at 6, 12, 18 and 24 months post baseline; also 6 and 12 months post intervention
Primary Outcome:	change in body weight (measured as a continuous variable) in the intervention group compared with the control group
Timepoint:	at 12 and 24 months post baseline; also 6 and 12 months post intervention
Secondary Outcome:	a decline in Edmonton Obesity status
Timepoint:	at 12 and 24 months post baseline, and 12 months post intervention

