Secondary Outcome:	change in absolute cardiovascular risk
Timepoint:	at 12 and 24 months post baseline, and 12 months post intervention
Secondary Outcome:	proportion of participants achieving individualised HbA1c targets according to the Australian Diabetes Society guidelines
Timepoint:	at 12 and 24 months post baseline; also 12 months post intervention
Secondary Outcome:	impact on psychometric scores as assessed using the Assessment of Quality of Life (SF-36), Patient Health Questionnaire (PHQ-9) [Depression] and Generalised Anxiety Disorder Assessment (GAD-7) [Anxiety], Assessment of Quality of Life (AQoL), Work Productivity and Activity Impairment (WPAI)
Timepoint:	at 6, 12, 18 and 24 months post baseline; also 6 and 12 months post intervention

Outcome measures and collection time points							
Measure	Base line	6 mth	12 mth	18 mth	24 mth	6 mth POST	12mth POST
Demographic and clinical measures:							
Demographic data, duration of diabetes	X						

 Demographic data, duration of diabetes at baseline only – to ensure similar characteristics of both the intervention and control groups. 							
Biometric measures; weight, BMI, girth, BP	X	X	X	X	X	X	X

 To review changes in metabolic parameters Time points to allow for intensification of treatment as deemed required Based on evidenced based guidelines/ peer-reviewed literature for timely treatment 							
Co-morbidities, medications	X		X		X		X

 To review changes (improvement/deterioration) in other co-morbidities as a result of treatment for obesity Review interval increased as changes in medication and disease profiles require review time, further based on timelines for review and assessment in peer-reviewed literature. 							
Edmonton obesity staging	X		X		X		X

 The Edmonton obesity staging system independently predicted increased mortality even after adjustment for contemporary methods of classifying adiposity (Padwal et al., 2011). The Edmonton obesity staging system may offer improved clinical utility in assessing obesity-related risk and prioritizing treatment. The project is targeting gradual weight loss that is linked to sustained weight loss – thus timing for assessment are linked to overall weight loss and potential co-morbidity reduction as estimated in peer reviewed literature 							
Sleepiness Scale	X		X		X		X

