 - HbA1c
 - Absolute cardiovascular risk
 - Psychometric measures (PHQ-9, depression and SF-36 Quality of Life)
 - Decline in Edmonton Obesity status (Padwal, 2011)
- Rationale - the power is in general a function of the possible distributions under the alternative hypothesis. As the power increases, the chances of a Type II error occurring decrease. We conducted power calculations to calculate the minimum sample size required using a target variance for an estimate to be derived from the sample eventually obtained.
- We assumed a Cohens d of 0.5 and a power of 0.95 based on estimates in the peer-reviewed literature.
- We assumed significance criteria of 0.05, the probability of the data implying an effect at least as large as the observed effect when the null hypothesis is true must be less than 0.05, for the null hypothesis of no effect to be rejected.
- Further, this assumed:
 - A follow-up period of at least 6 months for each participant.
 - Not all participants will be cared for simultaneously – there will be multiple intakes e.g. as people exit the program enrol new participants and controls.

Analysis TSRAC Q12

- Data will be exported from DiaBASE (Clinical software program) and entered into Excel (Microsoft) for data cleaning, then imported into Stata 12 and SPSS for analysis.
- Analysis will be performed using SPSS and Stata.
- Descriptive statistics will first be calculated to investigate the proportions of categorical variables and the distribution of continuous variables.
- Pearson's chi-square test or Fisher's exact tests will be utilized for investigation of associations between categorical variables, while independent t-tests will be used to investigate differences in continuous data between the control and intervention groups.
- For dichotomous outcomes logistic regression will be performed.
- For continuous outcome data analysis of covariance will be performed to test the effects of predictor variables.
- Adjusted relative risks (aRR) of metabolic and psychometric outcomes will be calculated for the control vs. intervention groups (with 95% confidence intervals) using a Poisson regression model with robust error variance.
- The regression models will include adjustment for age, pre-existing diabetes, socio-economic status and Asian or indigenous ethnicity.

Please provide additional justification on for the effect size with references.

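### Adjusted relative risks are assigned to metabolic and psychometric outcomes as a class, though most are continuous or scores, and the binary HbA1c-target outcome falls under two models with no rule for which is reported

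*Protocol*

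**What the plan says.** **Outcome definitions (Protocol, Outcomes).** The two primary outcomes are "change in HbA1c (measured as a continuous variable) in the intervention group compared with the control group" and "change in body weight (measured as a continuous variable) in the intervention group compared with the control group". The psychometric secondary outcome is "impact on psychometric scores as assessed using the Assessment of Quality of Life (SF-36), Patient Health Questionnaire (PHQ-9) [Depression" and further instruments; it has no event or responder threshold. One secondary outcome is plainly binary: "proportion of participants achieving individualised HbA1c targets according to the Australian Diabetes Society guidelines". Another is a decline in Edmonton obesity status, without a statement of what counts as a decline.

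**Analysis (Protocol, Statistical Analysis, Analysis TSRAC Q12).** Four statements matter here:

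- "independent t-tests will be used to investigate differences in continuous data between the control and intervention groups".
- "For continuous outcome data analysis of covariance will be performed to test the effects of predictor variables".
- "For dichotomous outcomes logistic regression will be performed".
- "Adjusted relative risks (aRR) of metabolic and psychometric outcomes will be calculated", by Poisson regression with robust variance, for control against intervention, with 95% confidence intervals.

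The regression models are to be adjusted for age, pre-existing diabetes, socio-economic status and ethnicity. The baseline value of the outcome is not on that list. No analysis is labelled primary.

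**Sample size (Sample Size TSRAC Q5).** 106 per arm, from Cohen's d of 0.5, power 0.95 and a significance level of 0.05.

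**The concern.** The relative-risk sentence applies to a whole class of outcomes, and most members of that class have no event whose risk could be compared. For HbA1c and weight it conflicts with the definitions in the Outcomes section. For the questionnaires it cannot be followed at all until somebody chooses a threshold. The sentence therefore cannot be read as covering only the binary secondaries, because no psychometric outcome is binary anywhere in the Protocol.

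Separately, the HbA1c-target outcome is both dichotomous and metabolic, so it qualifies for logistic regression and for Poisson regression. These report different quantities, and nothing says which is the result.

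At stake is the freedom left at analysis. The size of a relative risk for a continuous measure is set largely by where the cut is made, and dichotomising discards information. With no analysis named as primary, the plan does not say whether the mean difference or the ratio carries the conclusion. The relative risk is also the only analysis in the list for which confidence intervals are promised.

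**Working it through.** **1. Reproducing the sample size.** Inputs from the Protocol: d = 0.5, power 0.95, alpha 0.05 (sidedness not stated). For a two-sided comparison of two means:

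n per arm = 2(1.960 + 1.645)² / 0.5² = 2 × 12.996 / 0.25 ≈ 104.

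The t-distribution version gives 104.9, so 105. The stated 106 agrees with this, while a one-sided calculation gives 87 and does not. Power at 106 per arm is 0.952 (t) or 0.954 (normal). The stated size is that of a comparison of continuous means.

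**2. Which model applies to which outcome.**

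| Outcome | Scale in the Outcomes section | Models the analysis list assigns |
|---|---|---|
| HbA1c change, weight change | Continuous | t-test, ANCOVA, and relative risk if the class is read literally |
| PHQ-9, GAD-7, SF-36, AQoL, WPAI | Scores, no event | t-test, ANCOVA if treated as continuous, and relative risk |
| HbA1c target achieved | Binary, guideline threshold | Logistic and Poisson |
| Edmonton decline | Not stated to be binary | Unclear |

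PHQ-9 and GAD-7 bands do appear in Project Management under Diabetes Psychologist. There they set the number of psychology sessions and are not offered as outcome definitions. SF-36, AQoL and WPAI have no bands.

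**3. What dichotomising would do.** The Protocol gives no cut-point, so the control response rate p₀ is an assumption, varied from 10% to 70%. A normal outcome shifted by d = 0.5 gives p₁ = Φ(z(p₀) + 0.5). Then RR = p₁/p₀ (intervention over control), OR = [p₁/(1−p₁)]/[p₀/(1−p₀)], and with n = 106 per arm and p̄ the mean of p₀ and p₁:

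Power = Φ{ (p₁ − p₀ − 1.96√[2p̄(1−p̄)/n]) / √[(p₀(1−p₀) + p₁(1−p₁))/n] }.

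| p₀ (assumed) | p₁ | RR | OR | Power, 106 per arm | n per arm for 95% power |
|---|---|---|---|---|---|
| 10% | 21.7% | 2.17 | 2.50 | 0.65 | 250 |
| 30% | 49.0% | 1.63 | 2.24 | 0.81 | 169 |
| 40% | 59.7% | 1.49 | 2.23 | 0.83 | 164 |
| 50% | 69.1% | 1.38 | 2.24 | 0.82 | 168 |
| 70% | 84.7% | 1.21 | 2.38 | 0.73 | 208 |

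Worked line for p₀ = 50%: p₁ = Φ(0.5) = 0.691, RR = 0.691/0.5 = 1.38, OR = (0.691/0.309)/1 = 2.24.

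One unchanged effect therefore appears as a relative risk anywhere from 2.17 down to 1.21, depending on the cut. At a 50% control rate the Poisson model would report about 1.38 and the logistic model about 2.24. In the direction the Protocol writes, control against intervention, the same relative risk is 1/1.38 = 0.72, whereas the outcomes are phrased as intervention compared with control.

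**The case against.** The best defence is that the same list already gives continuous data a t-test and ANCOVA. Following the plan for HbA1c and weight therefore yields a comparison of means, and the relative risk is an addition that nothing labels primary. Responder thresholds for an additional analysis are commonly left to a SAP, which may exist here. Logistic and robust Poisson models are each valid for a binary outcome, and the HbA1c-target outcome has an external threshold, so a relative risk for it is legitimate.

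Much of this stands, and it rules out several stronger readings:

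- A reader might infer that the headline results depend on unstated cut-points, or that the primary analysis loses power. The documents do not show this, because the continuous analyses are listed alongside. The power losses above apply only where a dichotomised analysis is used in place of the continuous one.
- A reader might infer that thresholds will be chosen after the data are seen. The Protocol does not say so, and a SAP could fix them beforehand.
- A reader might say that the odds ratio will overstate the effect because events are common. The Protocol gives no event rates, and an odds ratio misleads only if it is read as a risk ratio.
- A reader might count Edmonton decline as a second outcome under both models. It is not stated to be binary, nor is it plainly metabolic or psychometric.
- The ANCOVA sentence does not list its covariates, so a baseline term is not excluded. It is only absent from the adjustment list that is given.

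The defence does not remove the conflict itself. The Protocol states an analysis that does not fit its own outcome definitions and assigns two effect measures to one outcome. A SAP would have to depart from or narrow that text rather than merely add detail.

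**Conclusion.** The point holds as an internal inconsistency that should be corrected. Relative risks are specified for a class that includes two continuous primary outcomes and several scores with no defined event. The HbA1c-target outcome has two competing models and no reporting rule. No analysis is named as primary, and the stated adjustment list omits the baseline value, which the trial collects.

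The size can only be illustrated. With 106 per arm and d = 0.5, power is 0.95 for the continuous comparison against about 0.65 to 0.83 if the same outcome is dichotomised. At an assumed 50% control rate the relative risk is about 1.4 and the odds ratio about 2.2. These figures rest on a normal outcome and assumed control rates of 10% to 70%. They show what the open choices could do, not a loss that the plan imposes on its primary outcomes.

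**What to change.** Amend the Analysis subsection in three respects:

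1. Restrict the relative risk to outcomes defined as binary: HbA1c target achieved, and Edmonton decline if it is defined as a drop of at least one stage.
2. Name one reported effect measure for those outcomes, either the relative risk or the odds ratio, and state its direction so that it matches the outcome definitions.
3. Name ANCOVA with the baseline value of the outcome as covariate, reporting adjusted mean differences with 95% confidence intervals, as the main analysis of HbA1c, weight and the scale scores.

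The cost is a few sentences of wording. No new data are needed, since baseline values of these measures are already scheduled.

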The multidisciplinary management of patients with obesity and type 2 diabetes is not straightforward. Although national diabetes guidelines recommend the use of laparoscopic banding procedures for patients with obesity who also have type 2 diabetes, the studies upon which this recommendation is based were conducted in patients with type 2 diabetes who had been diagnosed within 2 years of the laparoscopic procedure being performed (NHMRC, 2013). Evidence of effectiveness of surgery from randomised controlled trials in patients with type 2 diabetes of more than 2 years duration is not available.

Health problems related to excess weight impose substantial economic burdens on individuals, families and communities (Tanamas et al., 2013; Colagiuri, 2010). Data from the AusDiab study indicate that the total direct cost for overweight and obesity in 2005 was \$21 billion (\$6.5 billion for overweight and \$14.5 billion for obesity) (Tanamas et al., 2013; Colagiuri 2010). The same study estimated indirect costs of \$35.6 billion per year, resulting in an overall total annual cost of \$56.6 billion. A 1% absolute reduction in mean A1C levels has been associated with a 37% decrease in the risk of microvascular complications and a 21% reduction in the risk of any diabetes-related complication or death (UKPDS, 1998). Further, the 'legacy effect' providing long lasting effect; for all-cause mortality, the hazard ratio was 1 for years 0 to 10, but the risk reduction increased to 21% at year 15 and to 24.7% at year 20 (Livingstone & Fisher, 2007). Reduction in systolic blood pressure by 10mmHg also supporting reduction in end points related to diabetes and risk of death (Livingstone & Fisher, 2007; UKPDS, 1998).

The multidisciplinary management of patients with type 2 diabetes and obesity in rural and remote areas is not straightforward. Although national guidelines recommend multidisciplinary care, the availability of dietitian, psychologist and exercise physiologist supports in rural areas is limited. Further, the effectiveness of multidisciplinary management in rural areas has not been assessed. This is an important evidence gap as the built environment within which lifestyle modification must occur in rural areas is different to the environment within urban areas.

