- Following 3 months of lifestyle modification and intensive therapy if weight loss <5% Olistat will be introduced
- At 6 months participants will be referred to self-management program for ongoing behaviour modification
- For relevant cases at 12 months if weight loss not <5% and pathology demonstrates ketosis referral for surgical review
- Bariatric surgical assessment and patient counselling will be provided to determine:
 - whether surgery is indicated;
 - the patient's desire for, and likely tolerance to surgery; and
 - if so, what surgery type is most appropriate for the patient (Nguyen, 2013).

Following the completion of the up to 24 month program (the intervention) participants (both intervention and control) will be invited to continue to be part of the research project by way of providing follow-up data to determine sustainability of the intervention and project. Given Participants are existing patients of the service and will continue to be review as part of routine care at the Diabetes Centre, at their 24 month collection point (intervention and control) participants will be invited to continue with a collection of indicated markers at 6 and 12 months post intervention. If at their last visit (24 months) the participant indicates that they are happy for this to occur this verbal consent will be recorded on the spreadsheet used to collect project data – ie consent given: yes and date. If consent is provided by the participant, ongoing data will be collected following intervention period at 6 and 12 months post intervention.

Intervention Clarified/Differences in two arms of Study TSRAC QUESTION 12 (Response)

- Intervention of interest – **individualised** multidisciplinary multi-intervention assessment and treatment
- The impact of a model of care that assesses, triages and treats **all** factors impacting on metabolic processes from point of entry

Differences in two arms	
Control Group	Intervention Group

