
 1. Patient attends Diabetes Clinic 2. Pre-assessment includes physical measurements (BMI, BP) and HbA1c by CDE. Plus; Psychological Distress PHQ-9 and GAD-7, QoL SF-36v2, Assessment of Quality of Life (AQoL) and Work Productivity and Activity Impairment (WPAI). The above data will be collected by a research assistant and not the clinicians to prevent impact of 'treatment as usual'. 3. Patient reviewed by endocrinologist and management is diabetes and endocrine focused 4. Screening may include HbA1c, lipids, vitamin B12 and folates, TFTs, LFTs, ACR, eGFR 5. Referral to diabetes educator as needed for ongoing education if HbA1c above target 6. Referral to psychologist as required if patient raises psychosocial problems during consultations with either CDE or endocrinologist 7. Referral to dietitian if HbA1c > 9% in type 2 diabetes 8. Adhoc referral for bariatric assessment if BMI >40 and failed attempts at weight loss 	
 1. Patient attends AMOS Clinic 2. (a) Pre-assessment includes physical measurements (BMI, BP, girth) and HbA1c by CDE. (b) Universal screening - completion of scales to support planned assessment and care: 
 • Psychometric (Psychological Distress PHQ-9 and GAD-7, QoL SF-36v2 and AQoL, WPAI) • Epworth Sleepiness Scale • Absolute cardiovascular risk • Edmonton Obesity Staging (c) Review with physiotherapist for: 
 • Assessment for physical functioning performed • Completion of McCaffery Pain Assessment scale 3. (a) According to psychometric scales patient is triaged into psychologist for 1:1 or group session (b) Patient booked into physiotherapist for 1:1 or group sessions (c) According to dietitian assessment patient seen 1:1 or booked into group program (program facilitated by psychologist and dietitian with focus on identification of barriers) 4. Patient reviewed by endocrinologist and management is diabetes/endocrine and obesity focused 5. Screening for metabolic pathology request provided as per control group with addition of leptin and ketones (to identify weight loss and ketosis) and vitamin D In addition, assessment and review by dietitian to support development of treatment plan. 6. Treatment Plan agreed: 
 • Weight Loss goals determined • Referral as relevant to: 
 ○ Other health professional/specialist (sleep apnoea or pain management assessment if applicable) ○ Community Based Weight /Pain management programs (Stanford - GTMOL, OPAL) • Resistant or balance training • Medicines alteration and/or titration • Behaviours Modification and Self-Maintenance awareness 7. Initiation of Orlistat if BMI > 35 and < 2% weight loss after 3 months 8. Referral for bariatric assessment if deemed suitable and after 12 months failed treatment.

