Again although weight management is an important issue in the care of people with type 2 diabetes it is not the focus of the clinic; basic advice is provided in diet and physical activity by diabetes educators. Limited state funded dietetic services are utilised in the care of paediatrics with diabetes and generally adult individuals with type 1 and some with type 2 with pre-existing co-morbidities. Individuals with weight issues who are referred to state funded dietetic services for individualisation of advice are presented with a letter indicating that they ‘are not likely to be seen so will not be placed on a wait list’ and a list of private dietitians is provided. The same issue prevails as listed above in relation to financial capacity of the individuals. Thus, the majority of people with type 2 diabetes without co-morbidities or co-morbidities that are controlled, will not have personalised calculations of energy requirements needed and specific advice on the particular caloric decreased required to provide weight loss. In addition, the reasons behind eating behaviour and weight gain are more often from a psychology basis and/or related to funding of differing food types. Another limited health professional resource in the north west.

Methodology *(continue)*

Management of Cross Contamination TSRAC QUESTION 3 (Response)

- Randomisation will be achieved by method listed above
- Cross contamination is managed by several means:
 - The clinics are run on alternate days – thus patients are unlikely to come across each other – they may within the community as they would with any other RCT
 - The interventions which include multidisciplinary assessment and care, the use of orlistat and potentially bariatric surgery if identified as a suitable candidate requires assessment and referral – the control group patients will not have the assessments performed routinely and/or be in the setting to have these referrals created
 - The intervention group utilises a different credentialled diabetes educator than the ones used in the traditional (usual care) diabetes clinic
 - The endocrinologist involved in this study will mainly be involved in the AMOS clinic – during other clinics he will be seeing patients with type 1 diabetes of lower BMI who do not meet the criteria and due to different disease process their needs will differ
 - An alternate endocrinologist not involved in AMOS will see the control group within the traditional (usual care) diabetes clinic

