- Participants may directly benefit from participation in the study as a result of improvements in metabolic markers
- The early identification and management of secondary complications of obesity.
- A reduction in absolute cardiovascular risk.
- An improvement in glycated haemoglobin - or diabetes control.
- A potential reduction in body weight.

Risk of Harm

Low Risk – It is possible that participants may find some of the physical activities challenging and/or psychological sessions distressing. However, the study protocol directs those with higher levels of stress for therapies to reduce anxieties and distress. These are measured throughout the study at 6 month intervals.

Some participants will be referred for bariatric surgery. This surgery is associated with complications and adverse events. These are not a result of the study per se as the surgery is not experimental and is an established clinical treatment recommended in current national guidelines.

Other Risks

There are no foreseeable risks to the research team or the organisation.

Commercial Benefits of the Research for Investigators and Sponsors

There is no anticipated commercial benefit arising from the research for the investigators and/or sponsor

Risk of Harm as a Result of Dissemination

All data will be aggregated and de-identified and thus there is no foreseeable risk of harm when results are disseminated.

Mechanisms to monitor the Project

- The research will be conducted under the supervision of a steering committee comprised of members of the clinical team caring for the patients, experts in population health and with academic oversight.
- The clinic itself will operate under the supervision of the usual clinical governance of the North West Tasmanian Health Organisation (THO). All providers are staff members of THO North West, are credentialed to provide the clinical services outlined in the model and are subject to the safety and quality monitoring and reporting requirements of the North-West Regional Hospital, an accredited Australian public hospital.
- Regular monthly to 2 monthly meetings of the study investigators to monitor the conduct and progress of the study, and to manage change, problems and timelines.
- Meetings will review; participant recruitment rate, follow-up of participants according to key outcome timelines, reasons for attrition, data collection/entry and related issues, need for early termination of study.

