- Co-Principal Investigator/Project Manager will meet with Case Manager to identify any problems with follow-up and/or implementation of therapy plans.
- Study co-ordinator/Project manager will meet with recruiting staff to ensure training has been adequate and well supported for screening, recruiting and consenting of participants.

Data and Safety Monitoring

The likelihood of a serious adverse event occurring in this study is low and consequently there are no stopping rules. Given the short timeframe of this study 2.5 years it is unlikely that the issue of overwhelming benefit or futility will arise. Thus a Data and Safety Monitoring Board will not be established. Reports on Risk Assessment and Management will be provided to the Safety and Quality Committee of the THO on a 6 monthly basis.

Resources

Others Personnel Relevant to the Research Project

- [name]: Director Populations Health Operations- involved in the supporting of analysis of data to provide input in policy direction
- [name] (RN BN Diabetes Educator) /[name] (RN BN CDE): Research Assistant/Case Manager - ensuring participants receive care and therapies that have been planned, data collection and entry, and reviewing of data for completeness
- [name]: Manager of physiotherapy, provision of staffing for the study. May access the information to review factors that may relate to the role of the physiotherapist
- Surgeon TBA: Will provide assessment and review of patients deemed suitable for bariatric surgical procedures
- [name]: Manager of Pathology – involved in the provision of advice in pathology screening, will not access data
- [name]: Manager of the Diabetes Centre – involved in support clinics with staffing, will not access data – but may use final findings to change service delivery

Training

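### Surgical complications are declared not a result of the study although surgical referral is a step of the AMOS arm, and no harm is listed for comparison by arm

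*Protocol*

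**What the plan says.** **Surgery as part of the tested model.** The protocol's Management of Cross Contamination section refers to "The interventions which include multidisciplinary assessment and care, the use of orlistat and potentially bariatric surgery". The Study Intervention list includes, for relevant cases, "at 12 months if weight loss not <5% and pathology demonstrates ketosis referral for surgical review". The table of differences between the two arms gives as the last AMOS step "Referral for bariatric assessment if deemed suitable and after 12 months failed treatment". In the control column the matching entry is an ad hoc referral for patients with BMI above 40 whose attempts at weight loss have failed.

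**Attribution of harm.** Under Risk of Harm the protocol says that some participants will be referred for bariatric surgery and that "This surgery is associated with complications and adverse events". The next sentence reads "These are not a result of the study per se as the surgery is not experimental", and it adds that the surgery is established and recommended in national guidelines.

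**Monitoring.** Data and Safety Monitoring states: "The likelihood of a serious adverse event occurring in this study is low and consequently there are no stopping rules". No safety board is set up. A risk report goes to the hospital's safety and quality committee every 6 months.

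**What is collected.** The primary outcomes are change in HbA1c and change in body weight. The secondary outcomes and the collection table cover obesity staging, cardiovascular risk, HbA1c targets, psychometric scales, pain and function, laboratory markers, co-morbidities and medications, and referrals to health professionals.

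**The concern.** The protocol uses one test, whether a treatment is experimental, to decide whether its harm belongs to the study. For a randomised comparison of two models of care the relevant question is whether allocation changes who receives the treatment. Here it is meant to. A model that sends more people to surgical assessment may gain weight loss and lower HbA1c from those who go on to surgery. It may also bring the complications of that surgery. Both follow from the same step.

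As written, the gain is counted in the primary outcomes and the harm is assigned elsewhere and not tabulated. A report built on this plan could present the benefit of AMOS by arm without the matching harm. That matters because the protocol intends the model for wider use and expects to produce decision rules on when to refer for surgery.

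**Working it through.** The point rests mainly on reading sections against each other.

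1. **Does allocation affect exposure to surgery?** Yes, by design. The AMOS arm has a protocol step at 12 months (Study Intervention; step 8 of the arm-difference table). The control arm has ad hoc referral only. Management of Cross Contamination says that "the use of orlistat and potentially bariatric surgery if identified as a suitable candidate requires assessment and referral", and that control patients will not routinely have the assessments or be in the setting where such referrals arise. The 12-month trigger is worded differently in the Study Intervention list and in the table. The two need reconciling, but the point here does not depend on which is meant.

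2. **Is the difference all-or-none?** No. The arm-difference table and the section on orlistat and bariatric surgery both allow referral of control patients, and the protocol accepts that either arm may reach surgery through outside pathways. Exposure differs in degree.

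3. **Would any listed item capture the harm?** The nearest two would not.
   - Co-morbidities and medications are collected at baseline, 12 and 24 months and 12 months after the intervention. The stated purpose is to follow change in co-morbidities.
   - Referrals to health professionals are collected at baseline, 12 and 24 months. A referral is neither a procedure nor a complication.
   - No row covers adverse events, bariatric procedures, complications, reoperation, hospital admission or death, in either arm.

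4. **Does other oversight fill the gap?** The 6-monthly risk report is not described as by arm. The provision to account post hoc for outside treatment concerns treatments received, not harms.

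5. **Size.** The protocol gives no expected uptake of surgery and no complication rate, so no event rate can be derived. The only figure taken from it is 106 per arm, which reproduces closely for d = 0.5, two-sided alpha 0.05 and power 0.95: n = 2 × (1.960 + 1.645)² / 0.5² = 104 per arm by the normal approximation, and 105 by the t-test.

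   For scale only, with **assumed** rates, expected participants with a complication = 106 × uptake × complication rate:

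| Arm | Assumed uptake | Assumed complication rate | Expected number |
|---|---|---|---|
| AMOS, low | 5% | 5% | 106 × 0.05 × 0.05 = 0.27 |
| AMOS, high | 20% | 20% | 106 × 0.20 × 0.20 = 4.24 |
| Control, low | 0% | any | 0 |
| Control, high | 5% | 20% | 106 × 0.05 × 0.20 = 1.06 |

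   If uptake were 5% in both arms, the expected numbers would be equal. Whatever the true rates, no listed outcome would record the difference.

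**The case against.** The best defence is that the Risk of Harm section separates research-specific risk from the risk of established care, which is a normal distinction in an ethics submission. The protocol step is referral for assessment. Surgery comes later, depends on the surgeon's view and the patient's wish, and is also open to controls. Investigators meet every one to two months and review attrition and the need to stop early, and hospital safety reporting continues. Any events would be too few to test.

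Much of this stands, and it limits what can be said. A reader might infer several stronger things that the protocol does not support:

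- **That recording complications is forbidden.** The sentence is about cause and sets no rule on data collection. The gap comes from that sentence together with the outcome list, the schedule and the monitoring section.
- **That orlistat harms are also disclaimed.** The disclaimer covers surgery only. Orlistat belongs in the fix because it is part of the intervention, is not offered to controls, and has no adverse-event item.
- **That the low likelihood of serious adverse events is derived from the disclaimer.** The monitoring section neither mentions surgery nor refers back to Risk of Harm.
- **That the evidence gap in the background undercuts the claim of established treatment.** The sentence "Evidence of effectiveness of surgery from randomised controlled trials in patients with type 2 diabetes of more than 2 years duration is not available" concerns effectiveness, not safety, and stands beside a statement that national guidelines recommend banding.
- **That surgery is the main harm of the model, or that it occurs only in the AMOS arm.** No figure supports the first, and the referral routes for controls contradict the second.

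The defence does not answer the central point. Established treatment can still be given more often because of allocation, and monitoring that is not by arm cannot show whether that led to more harm. Small numbers are a reason for descriptive reporting, not for leaving events out.

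**Conclusion.** The concern holds in a limited form. The protocol treats surgery as a possible part of the intervention and then says its complications do not result from the study. Because exposure is designed to differ between arms, part of any surgical harm is a consequence of allocation. Neither the outcomes nor the schedule provides for comparing it.

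The effect is a possible one-sided account of benefit and harm. It is not an error in the primary analysis or the sample size. Its size is unknown: the range of 0.27 to 4.24 AMOS participants rests wholly on assumed rates. The conclusion does assume that the AMOS referral step leads to more surgery than usual care, which the protocol intends but does not quantify. This should be corrected in the protocol itself, because the attribution and the collection list are both fixed there.

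**What to change.** 1. Reconcile Study Intervention, the arm-difference table, Management of Cross Contamination, Risk of Harm, and Data and Safety Monitoring. Remove the statement that surgical complications are not a result of the study. A neutral replacement would be: *complications of bariatric surgery in participants of either arm are recorded and reported by randomised arm, although the surgery is established treatment.*
2. Add to the collection table, for both arms and with the same questions, serious adverse events, bariatric procedures with their complications, and orlistat-related adverse events, at the existing 6-monthly points. Include procedures done outside the service. Asking the same questions at the same times limits the chance that closer contact in the AMOS clinic alone produces more reports.
3. Report these descriptively by randomised arm in the final results and in the 6-monthly report already planned. After 24 months, state the number who agreed to further data collection, since that follow-up needs fresh consent.
4. Restate the sentence on the likelihood of serious adverse events so that it takes account of surgery.

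The cost is a short extra form at visits that already take place, the staff time to complete it, and the wording changes. The sample size, the primary outcomes and all referral and treatment rules stay as they are.
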